7.2 Study Procedures

Survey and HPV self-sampling kit

7.2. 1 10-14 days before/after the well-woman appointment

A study team member will obtain verbal consent from the participants to screen them for eligibility, and if they are eligible and agree to participate, a study team member will mail a self-sampling kit and summary explanation of research to be completed within 1 week.

7.2. 2 3-5 days before the Well-Woman appointment OR 13-21 days after Well-Woman appointment

Study physicians will perform the Pap smear/HPV test per standard clinical guidelines. Participants will complete the HPV self-sampling kit on their own time and mail it to the Penn State Health Clinical lab in a pre-labeled package provided by the study team.

3-5 days before the Well-Woman appointment: A study team member will call study participants to provide a reminder to attend their well-woman appointment (if necessary) and take a survey over the phone if they completed their HPV self-sampling kit. Those that did not complete the HPV self-sampling kit will get an appointment reminder (if needed) and be told not to use the self-sampling kit until after the Well-Woman appointment. They will be told they can complete the HPV self-sampling kit a week after their appointment.

13-21 days after Well-Woman appointment: For participants who did not complete their HPV self-sampling kit before their well-woman appointment, a study team member will call study participants to ascertain if they completed their HPV self-sampling kit and take a survey over the phone. If they still have not completed it or could not be reached, the study team will contact them up to 3 more times to gather information. Although participants must collect their sample within 21 days of their well-woman appointment, participants may be called up to seven days past day 14 in order to account for weekends and holidays and to give participants time to return phone calls if necessary. Participants will not be contacted after day 21.

7.3 Duration of Participation

Participants will be in the study for up to five weeks.

8.0 Subject Numbers and Statistical Plan

8.1 Number of Subjects

197

8.2 Sample size determination

Assuming $p < .05$ and $\beta > 0.80$, we need 197 participants to determine concordance/non-inferiority of test results across the two different methods using a Fisher's exact test and Cohen's kappa coefficient.

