1.0 Objectives

1.1 Study Objectives

The main objective is to compare the test characteristics of the Human Papillomavirus (HPV) self-sampling kit versus clinician-sampled HPV testing for cervical cancer screening. This study seeks to find out if the HPV self-sampling kit is non-inferior to standard clinician-sampling practices.

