3.3 Early Withdrawal of Subjects

3.3. 1 Criteria for removal from study

If the subjects does not complete the study activities they will be removed from the study. We don't anticipate clinician removal because study procedures are low risk.

3.3. 2 Follow-up for withdrawn subjects

The withdrawal will be documented and the subject will be replaced if the timeline allows

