4.2 Recruitment process

4.2. 1 How potential subjects will be recruited.

197 subjects will be recruited to participate in the protocol. Clinicians will identify participants they think would be eligible for the study and either provide some general information (via the recruitment cards and study flyers) to the participants or provide their contact information to the study team members so that they may contact the participant themselves. Members of the study team (both clinicians and non-clinical staff) will prospectively review clinic schedules in order to help identify potential participants, and clinicians may also identify patients after their scheduled appointment. This will ensure that enrollment numbers are met and that all potentially eligible participants are provided with a recruitment card and/or study flyer by their clinician or contacted directly by a study team member.

4.2. 2 Where potential subjects will be recruited.

Participants will be recruited at their well-women appointment in the clinician's office or over the phone by a study team member.

4.2. 3 When potential subjects will be recruited.

Potential subjects will be recruited by a clinician at participating clinics when they have a well-woman appointment or are making a well-woman appointment. Participants whose contact information was provided to study team members by the clinician or collected by another member of the study team will be contacted 10-14 days prior to their well-woman appointment. Participants who are given a recruitment card and/or study flyer will contact the study team if they are interested in participating. Participants who are contacted by the study team after their appointment will be contacted within 1-2 days of receiving their contact information from the clinician via the EMR.

4.2. 4 Describe the eligibility screening process and indicate whether the screening process will occur before or after obtaining informed consent. Screening begins when the investigator obtains information about or from a prospective participant in order to determine their eligibility. In some studies, these procedures may not take place unless HIPAA Authorization is obtained OR a waiver of HIPAA Authorization when applicable for the screening procedures is approved by the IRB. [For FDA regulated studies, consent for any screening activities would need to be obtained prior to screening unless specifically waived by the IRB.]

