7.0 Study Design and Procedures

7.1 Study Design

After identification, a study team member will talk with potential participants over the phone to determine those that meet the study eligibility criteria. HPV self-sampling kits, with the summary explanation of research, will be mailed to study participants to complete within a week.

If a participant is contacted prior to their well-woman appointment: 3-5 days before the well-woman appointment, the research project manager will reach out to check if study participants have completed their HPV self-sampling kit. Those that have completed the kit will complete a survey over the phone and get an appointment reminder. They will mail their HPV self-sampling kit to the Penn State Health clinical lab. Those that have not completed their HPV self-sampling kit will get instructions to not use the HPV self-sampling kit before the well-woman and get an appointment reminder. They will be told they can complete the HPV self-sampling kit one week after their appointment. If the first self-sampling kit is lost or not received, we will mail a second self-sampling kit. They will then go to their appointment where the clinician will perform the Pap smear/HPV test. If the participant did not complete the self-sampling kit, two weeks after the well-woman appointment a study team member will schedule a time to call the participant to determine if she completed the HPV self-sampling kit and, if so, complete a survey over the phone. If the participant is not able to be reached or has not completed the HPV self-sampling kit, the study team will perform up to three follow up calls per participant. Once an HPV self-sampling kit has been completed and the analysis has been received from the Penn State Health Clinical lab, study participants will be mailed their compensation within 1 week. Only one sample per participant will be mailed to the Penn State Health Clinical lab where they will receive and analyze each sample. Analysis of the self-sampling specimens will be conducted to determine HPV DNA positivity to compare to results of the previous Pap/HPV test. In the unlikely event that not enough sample is collected, the participant will still be compensated for their efforts, and the study team will take note of how much sample was deemed too little for analysis and they will be excluded from data analysis. EMR data will be used to check insurance status, and the date and result of PAP/HPV tests

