8.3 Statistical methods

We will conduct Fisher's exact tests to examine our primary study outcome, i.e., concordance/non-inferiority of HPV self-sampling test results versus clinician-sampled test results. Additional analyses of the concordance across test will use Cohen's kappa coefficient. In addition, we will summarize survey

results using descriptive analysis, including calculating means, Pearson's correlation coefficients, and Fisher's exact tests.

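### The 197 participants are justified for non-inferiority through Fisher's exact test, which as planned cannot show it, and nothing stated supports the implied 80% power

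*Combined protocol and SAP*

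**What the plan says.** Section 1.1 sets the question: "This study seeks to find out if the HPV self-sampling kit is non-inferior to standard clinician-sampling practices". Section 8.2 gives the whole sample-size justification in one sentence: "we need 197 participants to determine concordance/non-inferiority of test results across the two different methods using a Fisher's exact test". Kappa is named there as a second method, and the only inputs given are a significance level of .05 and a power term written as β > 0.80. Section 8.3 carries the choice into the analysis: "We will conduct Fisher's exact tests to examine our primary study outcome", with kappa as an additional analysis.

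The data are paired. Section 7.1 says: "Analysis of the self-sampling specimens will be conducted to determine HPV DNA positivity to compare to results of the previous Pap/HPV test".

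On losses, 197 is also the recruitment target in Section 4.2.1 ("197 subjects will be recruited to participate in the protocol"). Section 3.3.2 says of a withdrawal that "the subject will be replaced if the timeline allows". Section 7.1 excludes insufficient samples from the analysis, calling them unlikely, and mentions no replacement for them.

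**The concern.** A non-inferiority claim needs a margin and a confidence limit to set against it. The plan names a test that uses neither, and sizes the study on it.

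Section 8.2 also mislabels power: β is the type II error, so β > 0.80 read literally means power below 20%. Presumably 80% power was meant, and that reading is used below. Beyond that and the significance level, 8.2 gives no margin, scale, sidedness, expected positivity, discordance or kappa hypothesis.

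At stake is the main conclusion. With no decision rule written down, a significant Fisher result on one table, or a non-significant one on the other, could be reported as meeting the objective even if self-sampling misses many of the women the clinician sample detects. A reader also could not tell what loss of detection 197 pairs were able to exclude.

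**Working it through.** **Inputs.** From the documents: N = 197, α = 0.05 (sidedness not given), implied power 80%, paired results. Positivity, kappa, discordance, margins and loss rates below are assumptions, because the documents give none.

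**Can 197 be reproduced?** No formula can be evaluated from α and power alone. Unrelated assumptions land on or next to it:
- 15% v 25%, one-sided, unpaired: 197 per group.
- Paired non-inferiority, discordance 8%, 5-point margin, one-sided 0.05: 6.183 × 0.08 / 0.05² = 197.9, so 198.
- One-degree-of-freedom association test, effect size w = 0.2: 7.849 / 0.2² = 196.2, so 197. This tests association only.

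**What Fisher's test does with these data.** Take 10 women positive on both samples, 10 on the clinician sample only, 0 on the self-sample only and 177 negative on both.

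| Analysis | Result |
|---|---|
| Fisher, cross-table | p = 9.6e-12 |
| Kappa | 0.64 |
| Fisher, 10/197 v 20/197 | p = 0.086 |
| Exact McNemar, 0 of 10 discordant | p = 0.002 |
| Paired difference, -10/197 | -5.1 points (95% CI -8.1 to -2.0) |
| Relative positivity, 10/20 | 0.50 (95% CI 0.32 to 0.78) |

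The ratio interval is log-Wald with SE = sqrt(10/(10 × 20)) = 0.224. The cross-table test responds to any association: complete disagreement (0/98/99/0) gives p of about 9e-59.

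The example is not a freak. In 20,000 simulated trials per setting, with the self-sample truly finding half of clinician-positives and no others:

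| Positivity | Cross-table significant | Method by result not significant |
|---|---|---|
| 5% | 99% | 95% |
| 10% | >99% | 68% |
| 15% | 100% | 33% |
| 20% | 100% | 11% |

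**What 197 pairs deliver in a paired non-inferiority test.** With true difference 0 and one-sided 0.025, power = Φ(margin / sqrt(D/197) − 1.960), where discordance D = 2p(1−p)(1−κ). For p = 10% and κ = 0.6, D = 2 × 0.1 × 0.9 × 0.4 = 0.072, so a 5-point margin gives Φ(0.05 / sqrt(0.072/197) − 1.960) = 74%.

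| Positivity | D, κ = 0.6 | Power, 5 points | D, κ = 0.8 | Power, 5 points |
|---|---|---|---|---|
| 5% | 0.038 | 95% | 0.019 | >99% |
| 10% | 0.072 | 74% | 0.036 | 96% |
| 15% | 0.102 | 59% | 0.051 | 87% |
| 20% | 0.128 | 50% | 0.064 | 79% |

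Simulation agrees within about two points (for example 93% rather than 95% in the first cell). The largest discordance that still gives 80% power is 197 × 0.05² / 7.849 = 6.3%.

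Scale matters as much as the margin. Five points is the whole positive rate at 5% positivity, half of it at 10% and a quarter at 20%. A 10-point margin gives at least 97% throughout, but at 5 or 10% positivity it equals or exceeds the whole positive rate. With a relative-positivity margin of 0.80, simulated power at κ = 0.6 / 0.8 is 23 / 41% at 10% positivity and 43 / 69% at 20%.

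**Precision at 197.** Positive agreement of 18/20 has exact 95% CI 68 to 99%; 35/39 has 76 to 97%. At 10% positivity, kappa has a half-width of 0.19 at κ = 0.6 and 0.14 at κ = 0.8.

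**Losses.** If 197 gave exactly 80%, an unreplaced loss L leaves Φ(2.802 × sqrt(1−L) − 1.960): 78% at L = 5% (187 pairs) and 76% at L = 10% (177 pairs).

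**The case against.** The best counter-arguments are these:

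- **Fisher's framework can yield an interval.** For 10/197 v 20/197 the odds ratio is 0.47 (95% CI 0.19 to 1.10), and such a limit could be held against a margin. That is true in principle, but the plan specifies neither interval nor margin, and the interval would still ignore the pairing.
- **Kappa is also named and does use the pairing.** It addresses the concordance half of the stated outcome. It has no threshold here, though, and does not isolate a shortfall in the self-sample's direction: it reads 0.64 when half of the positives are missed.
- **The plan never says that either Fisher result would be declared non-inferiority.** Correct. The misreading is a risk rather than a stated rule, but the plan supplies no valid rule in its place.
- **The half-detection case is a chosen stress case.** It is, and it is labelled as an assumption. The fault in the method does not depend on it.
- **No number in 8.2 is shown to be wrong, and 197 may be ample.** This stands. The fault lies in the method and the missing inputs.
- **Losses are limited** by a second kit, follow-up calls and conditional replacement. This stands too, so the lack of inflation is minor.

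**Conclusion.** The concern holds, and the plan is wrong as written on its main objective. Fisher's test as specified cannot establish non-inferiority on either table it could be run on, and the implied 80% power has no stated basis. This conclusion needs no outside figure: it follows from the paired design, the non-inferiority aim and the absence of any margin.

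The size does rest on assumptions. For a 5-point margin, power at 197 lies between 50% and over 99% across positivity of 5 to 20% and kappa of 0.6 to 0.8, assuming equal true positivity and one-sided 0.025. The number 197 is therefore unsupported, not shown to be inadequate. The β label and the absence of an allowance for losses are lesser points.

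**What to change.** In 8.2, write power as 1−β and stop attributing non-inferiority power to Fisher's test. In 8.3, make the primary analysis a confidence interval for the paired difference or for relative positivity, on women with both HPV results. Report positive agreement, negative agreement and kappa with 95% CIs. Section 1.2 also mentions Pap results, so state that the HPV pair carries the primary comparison. Then choose one route:

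- **(a) Keep non-inferiority.** State a margin and its scale, justified on clinical or screening grounds independently of 197. Add sidedness and mutually compatible positivity and discordance, and report whatever power 197 gives.
- **(b) Restate 197 as precision-based.** Give expected interval widths over a range of positivity, limit 1.1 to estimating agreement, and remove the non-inferiority wording from 8.2 and 8.3.

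Under either route, report power or precision at the expected number of evaluable pairs as well as at 197.

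The cost is text in 8.2 and 8.3, plus 1.1 under (b), and a clarification of the primary comparison. No new data or added enrolment is required. The price is candour: a 5-point margin with 10% discordance gives 60% power at 197, and 80% would take 7.849 × 0.10 / 0.05² = 314 pairs at one-sided 0.025, or 6.183 × 0.10 / 0.05² = 248 at one-sided 0.05.

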8.3 Statistical methods

We will conduct Fisher's exact tests to examine our primary study outcome, i.e., concordance/non-inferiority of HPV self-sampling test results versus clinician-sampled test results. Additional analyses of the concordance across test will use Cohen's kappa coefficient. In addition, we will summarize survey

results using descriptive analysis, including calculating means, Pearson's correlation coefficients, and Fisher's exact tests.

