1.2 Primary Study Endpoints

The primary outcomes of this study are to analyze the screening results on self-sampling kits compared to clinician-collected HPV test and Pap smear results.

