6.2 Waiver or Alteration of Authorization for the Uses and Disclosures of PHI

6.2. 1 Access, use or disclosure of PHI representing no more than a minimal risk to the privacy of the individual

6.2 .1.1 Plan to protect PHI from improper use or disclosure

Information is included in the "Confidentiality, Privacy and Data Management" section of this protocol.

6.2 .1.2 Plan to destroy identifiers or a justification for retaining identifiers

Identifiers will be destroyed after the completion of data collection.

6.2. 2 Explanation for why the research could not practicably be conducted without access to and use of PHI

The proposed study requires enrollment of participants who are getting a clinical Pap/HPV test to compare those results with the findings from a self-sampled HPV test. Identification of these patients would be infeasible using other methods.

6.2. 3 Explanation for why the research could not practicably be conducted without the waiver or alteration of authorization

The waiver is necessary in order to screen participants for eligibility using the patient's medical record prior to their consent to participate in this study. This method will allow study team members to efficiently identify patients who are receiving/have received a Pap/HPV test. Many well-woman exams do not require a Pap/HPV test and it is not practical to provide information to all of these patients.

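### Section 8.3 assigns a paired concordance/non-inferiority outcome to Fisher's exact test, which cannot test non-inferiority, and the plan gives no margin or success rule

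*Combined protocol and SAP*

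**What the plan says.** Section 1.1 sets the aim: "This study seeks to find out if the HPV self-sampling kit is non-inferior to standard clinician-sampling practices". The sentence before it names clinician-sampled HPV testing as the comparator. Section 1.2 gives the primary outcomes, in the plural, as to "analyze the screening results on self-sampling kits compared to clinician-collected HPV test and Pap smear results", without ranking the two comparators.

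The design is paired. Section 6.2.2 says the study needs "participants who are getting a clinical Pap/HPV test to compare those results with the findings from a self-sampled HPV test". Section 7.1 adds: "Analysis of the self-sampling specimens will be conducted to determine HPV DNA positivity to compare to results of the previous Pap/HPV test". Section 7.4.3 marks assignment to groups as not applicable.

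Section 8.3 names the primary analysis: "We will conduct Fisher's exact tests to examine our primary study outcome, i.e., concordance/non-inferiority of HPV self-sampling test results versus clinician-sampled test results". It continues: "Additional analyses of the concordance across test will use Cohen's kappa coefficient". Section 8.2 says 197 participants are needed "to determine concordance/non-inferiority of test results across the two different methods using a Fisher's exact test and Cohen's kappa coefficient". It gives p<.05 without sidedness, and writes 0.80 as beta where power is apparently meant. Sections 8.2 and 8.3 read as complete, with no sign of redaction.

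**The concern.** A non-inferiority conclusion needs three things: a parameter, a margin on that parameter, and a rule linking a confidence limit to the margin. The plan gives none of them, and the test it names has no margin in its null hypothesis. The plan also does not say which table Fisher's test is applied to, and the two possible tables answer different questions.

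Without a written rule, the basis for calling self-sampling non-inferior could be chosen after the results are seen. The chance of a false claim is then uncontrolled. Section 11.2 says similar findings could support self-sampling for women without routine access to care, so a false claim would have consequences.

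**Working it through.** **The plan's own figure.** 197 cannot be reproduced, because section 8.2 gives no positivity rate, margin, discordance or kappa value. Several unrelated independent-group assumptions land near it at 80% power: 15% vs 25%, one-sided 0.05, gives 197 per arm; 10% vs 20%, two-sided, gives 199 per arm; non-inferiority at 20% with a 10-point margin, one-sided 0.05, gives 198 per arm. None of these inputs is in the documents. This does not show that 197 is wrong, only that it cannot be checked.

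**What a paired margin would need.** With a true difference of 0, n = (z₁₋α + z₀.₈₀)² × (discordant share) / margin². At one-sided 0.025 the squared term is (1.960 + 0.842)² = 7.85. With an assumed 10% discordance and a 5-point margin, n = 7.85 × 0.10 / 0.0025 = 314 pairs. With 197 pairs, the smallest margin with 80% power is 2.80 × √(discordance/197): 4.5, 6.3, 7.7 and 8.9 points at 5%, 10%, 15% and 20% discordance.

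**One table worked through.** Assume 10% prevalence: 197 × 0.10 ≈ 20 clinician positives. Suppose self-sampling finds 10 of them and adds no positives. The counts are 10 both positive, 10 clinician only, 0 self only, 177 both negative.

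- Fisher on the cross-table: p = 9.6 × 10⁻¹². This is strong association, although half the positives were missed.
- Fisher on 20/197 vs 10/197 as if independent: p = 0.086.
- Exact McNemar on the same data: p = 0.002.
- Paired difference: (10 − 20)/197 = −5.1 points; SE = √(10 − 10²/197)/197 = 1.56 points; 95% CI −8.1 to −2.0.
- Kappa: observed agreement 187/197 = 0.949; chance agreement (20×10 + 177×187)/197² = 0.858; kappa = (0.949 − 0.858)/(1 − 0.858) = 0.64.

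In a second table (6, 14, 14, 163), positive agreement is 6/20 = 30% and kappa is 0.22. Cross-table Fisher is still significant (p = 0.008), and Fisher on the rates gives p = 1.

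**Simulation.** 197 pairs, 20,000 replicates per scenario. Prevalence (share positive on the clinician test), positive agreement (PPA) and negative agreement (NPA) are all assumed. The poor self-test has PPA 50%. Entries are for 5/10/15/20% prevalence.

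| NPA | Cross-table p<.05 (% of trials) | Rates p≥.05 (% of trials) |
|---|---|---|
| 100% | 99.1 / 100 / 100 / 100 | 94.5 / 68.2 / 33.3 / 10.5 |
| 98% | 95.6 / 99.8 / 100 / 100 | 99.7 / 93.4 / 71.3 / 38.1 |
| 95% | 91.1 / 99.3 / 100 / 100 | 94.1 / 99.5 / 94.9 / 76.7 |

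A good self-test (PPA 90%) gives cross-table p<.05 in 99.9% to 100% of trials, so a significant cross-table result barely distinguishes the two. The rates comparison misleads mainly at low prevalence or lower NPA. At 5% prevalence and NPA 95%, the poor test is non-significant more often (94.1%) than the good one (80.8%). Kappa does separate them: at 10% prevalence and NPA 100/98/95% it is 0.64/0.56/0.46 for the poor test and 0.94/0.85/0.74 for the good one.

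**The case against.** The best defence is that this is a small concordance study and that kappa, a proper paired measure, stands beside Fisher's test in the sample-size section. That part stands. A reader might infer that the plan has no valid analysis of concordance, and the documents do not support this. The failure is in the non-inferiority half and in the missing threshold. Kappa does not repair the non-inferiority half: section 8.3 calls it additional, and being symmetric it does not show whether self-sampling misses clinician positives.

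A reader might also infer that section 1.2 merges HPV and Pap results into one outcome, or that the comparator is unknown. Section 1.2 speaks of outcomes in the plural, section 8.3 of tests in the plural, and section 1.1 points to the clinician HPV test. What remains is two unranked comparators.

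It is likewise tempting to read the simulated percentages as this plan's error rates. They are not: every input is assumed, missing half the positives is an extreme case, and no section says that p≥.05 would count as success.

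Finally, section 2.1 mentions guidelines that allow cytology and/or HPV testing, and section 3.1 requires only an in-office screening. A reader might conclude that some participants will lack a clinician HPV result. That is possible, but the documents do not establish it.

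**Conclusion.** The point holds and should be corrected before the data are reviewed. The argument is logical and needs no assumed figures: the data are paired, neither use of Fisher's test has a non-inferiority null hypothesis, and no section supplies a margin, confidence-limit rule, kappa threshold or other criterion. The objective in section 1.1 therefore cannot be answered by the analysis in section 8.3. A false claim of non-inferiority is a risk and not a certainty, because no success rule is written. The simulations and example tables only illustrate how uninformative the named test can be under assumed prevalence and agreement. The ranking of the Pap comparison is a smaller matter. Nothing here shows that the non-inferiority aim must be withdrawn; that depends on whether a margin or floor can be justified and supported by 197 women.

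**What to change.** 1. In 8.2 and 8.3, replace Fisher's test as the primary analysis. Use positive percent agreement with the clinician HPV result, with an exact 95% CI, in women with both HPV results. Report with it negative percent agreement, kappa with a CI, and the paired positivity difference with a score (Tango) CI. Fisher's test can stay for unpaired survey comparisons.
2. In 1.2, make the clinician HPV comparison primary and the Pap comparison secondary.
3. To keep the non-inferiority claim, name one paired estimand: positive agreement against a floor, or the positivity difference against a margin. Fix and justify the floor or margin and the one-sided alpha before data review, and restate in 8.2 what 197 women can support.
4. If no floor or margin can be justified, or 197 cannot support it, reword 1.1, 8.2 and 8.3 as estimating agreement.
5. Report how many women lack a clinician HPV result or gave too little sample. Section 7.1 already notes "how much sample was deemed too little for analysis and they will be excluded from data analysis".

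**Cost.** No new procedures are needed, since section 7.1 already takes Pap/HPV results from the medical record. Step 4 would give up a stated objective, which is more than an edit. If the sample size changed, 4.2.1, 8.1 and 15.2 would also need amending.

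**Downsides**, all under assumed inputs:
- With about 20 clinician positives (10% prevalence), intervals are wide: 18 of 20 gives 68% to 99%, and 10 of 20 gives 27% to 73%.
- With an illustrative 80% floor (exact lower 95% limit above 80%), a test with 90% true agreement passes in only 0.3%, 10% and 30% of trials at 5%, 10% and 20% prevalence.
- A positivity-difference margin separates well in some settings. At 10% prevalence, NPA 98% and a 5-point margin, the 90%-agreement test passes in 98% of trials and the 50% test in 14%. At 5% prevalence with the same NPA and margin, the 50% test passes in about 72%.
- Positive agreement treats the clinician result as the reference, so it measures agreement and not accuracy.

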2.3 Study Rationale

The impact of the proposed project is to compare HPV self-screening results with Pap smear results, clinician-collected HPV test to ultimately improve the uptake of HPV screening. This study will be conducted in a normal risk population.

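### The planned analysis of the test results (Fisher's exact test, plus Cohen's kappa as the only agreement statistic) cannot tell clinician-positives missed by self-sampling from extra self-sample positives

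*Combined protocol and SAP*

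**What the plan says.** The objective in section 1.1 has a direction: "The main objective is to compare the test characteristics of the Human Papillomavirus (HPV) self-sampling kit versus clinician-sampled HPV testing", with non-inferiority of the kit as the stated aim.

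Section 8.3 gives two methods for the test results. The primary one is: "We will conduct Fisher's exact tests to examine our primary study outcome, i.e., concordance/non-inferiority of HPV self-sampling test results versus clinician-sampled test results". The second is: "Additional analyses of the concordance across test will use" Cohen's kappa. The remaining methods in that section (means, Pearson correlations and further Fisher's tests) are for the survey.

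Section 8.2 rests the sample size on the same two methods: "we need 197 participants to determine concordance/non-inferiority of test results across the two different methods".

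Neither section mentions sensitivity, specificity, positive or negative percent agreement, or the two discordant counts. No benchmark for kappa is set. On the expected number of positives, the plan offers only the remark in section 2.3: "This study will be conducted in a normal risk population". No prevalence is given.

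**The concern.** Each woman supplies both samples, so the HPV results form a paired 2×2 table. Its two discordant cells mean different things. One holds women positive on the clinician sample and negative on their own, which are potential missed screens. The other holds women positive only on their own sample, which are extra detections or false positives. A non-inferiority question turns mainly on the first cell; a description of test characteristics needs both, kept apart.

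Kappa merges the two cells, and Fisher's test asks only whether the two results are associated. A report that follows section 8.3 to the letter could therefore give identical output for a self-sample that misses 30% of clinician-positives and for one that misses none. Section 11.2 looks ahead to self-sampling for women without routine access to preventive care, where missed positives are the costly error.

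**Working it through.** **Inputs.** From the documents: 197 women (sections 8.1 and 8.2), each giving both samples (section 7.1); Fisher's exact test and kappa (section 8.3). Not in the documents, so assumed: the number of clinician-positives (20 of 197, about 10%, in the main example; 5% to 30% as a range) and the number of discordant pairs. I take 197 complete pairs; section 7.1 excludes inadequate samples, so the real number may be smaller.

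**The plan's own figure.** The 197 cannot be reproduced from what section 8.2 states, because it gives no effect size, margin, prevalence or kappa values. A 1-df chi-square with an assumed effect size w = 0.20 gives (1.960 + 0.842)² / 0.20² = 196.2, so 197. A test of kappa 0 against 0.20 also gives 197. The recruitment arithmetic in section 15.2 gives 0.25 × 790 = 197.5. None of these can be confirmed as the source.

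**Formulas.** Let a = both positive, b = clinician-positive only, c = self-positive only, d = both negative, and N their sum.

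- Observed agreement: po = (a + d)/N
- Chance agreement: pe = [(a + b)(a + c) + (c + d)(b + d)]/N²
- Kappa = (po − pe)/(1 − pe)
- Positive percent agreement (PPA) = a/(a + b); negative percent agreement (NPA) = d/(c + d)

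Exchanging b and c leaves po and pe unchanged, so kappa is unchanged at any prevalence. The exchange transposes the table, so Fisher's p-value is unchanged too.

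**Table 1: 20 clinician-positives, 6 missed, none added (14, 6, 0, 177).**

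- po = 191/197 = 0.970
- pe = (20 × 14 + 177 × 183)/197² = 32,671/38,809 = 0.842
- Kappa = (0.9695 − 0.8418)/(1 − 0.8418) = 0.81 (large-sample 95% CI 0.66 to 0.96)
- Fisher p = C(20,14)/C(197,14) = 4 × 10⁻¹⁷
- PPA = 14/20 = 70% (exact 95% CI 46% to 88%); NPA = 177/177 = 100%

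**Table 2: the mirror (14, 0, 6, 177).** There are now 14 clinician-positives, none missed, and 6 self-only positives.

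- Kappa 0.81 and Fisher p = 4 × 10⁻¹⁷, as in Table 1
- PPA = 14/14 = 100%; NPA = 177/183 = 96.7%

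**How far the high kappa depends on the example.** Keep 20 clinician-positives and 6 misses (PPA 70%) and add self-only positives:

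| Self-only positives | Kappa |
|---|---|
| 0 | 0.81 |
| 2 | 0.76 |
| 4 | 0.71 |
| 6 | 0.67 |
| 9 | 0.61 |

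With 30% missed and no self-only positives, kappa is 0.82, 0.81, 0.80, 0.79 and 0.76 for 10, 20, 30, 40 and 60 clinician-positives. Fisher's p is below 10⁻⁶ in every one of these tables.

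**Prevalence, a separate matter.** With PPA fixed at 85% and NPA at 97%, kappa is 0.68 at 5% prevalence, 0.78 at 10% and 0.84 at 30%. The same test performance gives different kappas.

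**Precision of PPA if 90% is observed (exact 95% CI).** 18/20: 68% to 99%. 27/30: 73% to 98%. 36/40: 76% to 97%.

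**The case against.** Four points can be made for the plan.

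First, section 8.3 makes kappa an additional analysis, with no threshold or decision rule, so no conclusion formally hangs on it. That is correct, and kappa should not be described as the study's headline test. The primary test does not fill the gap, however, because Fisher's p-value is the same for both mirror tables.

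Second, kappa corrects for chance agreement and does respond to misses. This stands. With 20 clinician-positives and no self-only positives, missing 10 gives kappa 0.64, and missing all 20 gives 0 although raw agreement is still 177/197 = 90%. A reader might infer that kappa stays high whatever happens among the positives; that would be true of raw agreement, which the plan does not propose. Kappa's defect here is that it falls equally for either kind of disagreement.

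Third, the 0.81 is a favourable case. It needs no self-only positives, and the mirror table also changes the clinician-positive count from 20 to 14. Both facts limit the example. The symmetry itself is algebra and does not depend on them.

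Fourth, no histological reference is planned, so a symmetric summary is not unreasonable as a supplement, and the investigators could compute positive agreement from the same table. Both are fair, but nothing in the plan commits them to doing so, and self-only positives matter for the test-characteristics objective as well.

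**Conclusion.** The point holds in a limited form. As written, the analysis of the test results has no directional component: kappa and Fisher's p-value are identical for a self-sample with PPA 14/20 and for its mirror with PPA 14/14. The symmetry needs no assumption. The size of the illustration rests on an assumed 20 clinician-positives, 197 complete pairs and no self-only positives. With 2 to 9 self-only positives, the same 30% miss goes with kappa of about 0.76 to 0.61. High kappa alongside 30% missed can therefore occur, but is not to be expected in every case, and any label such as strong would come from an outside scale that the plan does not adopt.

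A reader might also infer from the normal-risk population that low prevalence inflates kappa and so hides the misses. The figures do not support this. At fixed PPA 85% and NPA 97%, kappa is lower at low prevalence (0.68 at 5%, 0.84 at 30%). Prevalence makes kappa hard to interpret; it is the symmetry that conceals the direction.

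This should be corrected, but it ranks below the absence of a margin and of a paired primary test, which are separate defects.

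**What to change.** In section 8.3, make positive and negative percent agreement of the self-sample against the clinician HPV result, each with an exact 95% CI, the main concordance results. Report the two discordant counts separately. Keep kappa as a descriptive supplement.

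In section 8.2, state the number of clinician-positives expected among 197, as an assumption with a range, and the resulting interval width for positive agreement. For example, 90% observed with 20 positives spans 68% to 99%, and with 40 positives 76% to 97%.

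The cost is wording only: no new data, women or procedures. The drawback is that the positive-agreement interval will be wide and will look less favourable than a single kappa. The change also treats the clinician sample as the reference, which should be said. It does not resolve the missing non-inferiority margin or the lack of a paired primary test; those need their own amendment.
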